## 2. METHOD

### 2.1. Study Design

Based in a university clinic, youth will be randomly assigned, stratified by sex and age (10-14, 15-18), in a 1:1 parallel group design, to receive either TranS-C or PE. Sibling pairs will be randomized to the same condition.

Assessors will be blind to treatment allocation. Sequentially numbered, opaque, sealed envelopes will be generated using a computer-generated random number list. A project coordinator will conduct randomization after all eligibility assessments are completed. Assessments will be conducted at baseline and at the end of treatment. The Committee for the Protection of Human Subjects approved the study.

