### 2.2. Participants

Participants will be recruited through clinicians or advertisements. Individuals will be eligible if they (a) are between 10 and 18 years old, living with a parent or guardian, and attending a class/job by 9am at least 3 days per week; (b) are fluent in English; (c) are able and willing to give informed assent; and (d) report eveningness as demonstrated by scoring within the lowest quartile of the Children's Morningness-Eveningness Preferences Scale (CMEP; 27 or lower) and have a 7-day sleep diary showing a sleep onset time of 10:40pm or later for 10-13 year olds, 11pm or later for 14-16 year olds, and 11:20pm or later for 17-18 year olds at least 3 nights per week. In addition, this sleep pattern will have to have been present for the past 3 months. Finally, participants will have to fall into an 'at risk' range on measures of at least one of the five health domains reviewed above.

Exclusion criteria will be (a) an active, progressive physical illness or neurological degenerative disease directly related to the onset and course of the sleep disturbance; (b) evidence of obstructive sleep apnea, restless legs syndrome, or periodic limb movement disorder; (c) significantly impairing pervasive developmental disorder; (d) bipolar disorder, schizophrenia, or another current Axis I disorder if there is a risk of harm if treatment is delayed. Participants will cease taking medications that alter sleep (e.g., hypnotics) 4 weeks prior to the assessment (2 weeks for melatonin) or will be excluded. Finally, history of substance dependence in the past six months or current suicide risk sufficient to preclude treatment on an outpatient basis will be exclusionary.

In other words, receipt of another sleep treatment will be the only type of treatment excluded. We want to be sure that any improvements in sleep could be attributed to TranS-C or PE, not the other sleep treatment. Other medications will be allowed. A medication-free group would be unrepresentative. We will also include youth with Axis I psychiatric comorbidity (except for bipolar disorder and schizophrenia), even if they are receiving treatment for that comorbidity.

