### **2.3.2. Psychoeducation (PE)**

Psychoeducation (PE) is an active comparison treatment associated with sleep improvement. PE constitutes a conservative control for treatment location, experience and skill level of the therapists, the number and quality of handouts, therapist attention, amount and frequency of contact with the therapist, duration of treatment, and beliefs and expectations about the efficacy of treatment held by the teens. Sessions will focus on the inter-relationship between sleep, stress, diet, health, exercise, accidents, and mood. These sessions will involve obtaining a detailed description from the teen about their experience with the topic and general education. Participants will also be given the choice of sampling meditation, yoga, and/or outdoors appreciation. There will be no explicit focus on sleep except briefly mentioning sleep as a common contributor to each topic. If a participant raises issues related to sleep or requests

advice on implementing change, the therapist will respectfully return to the content of the session. The emphasis will be on providing information but not on specifically facilitating behavior change.

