After the overnight, the participant will be randomized and complete a further 7 night sleep diary and answer phone calls to collect Ecological Momentary Assessment (EMA) data. This additional sleep diary will be collected so that sleep diary data will be concurrent with EMA. These measures will be the basis of the primary and secondary outcomes. Treatment will commence one week later.

After treatment, the procedures for the overnight assessment to collect DLMO will be repeated, along with an in-person interview and 7-days of EMA and sleep diary. The participants will be reimbursed \$30 for participating in the pre- and post-treatment assessments and \$40 for the 6-FU and 12-FU. Parents will be reimbursed \$30 for participating in the pre- and post-treatment assessments, \$20 for the 6-FU, and \$20 for the 12-FU.

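### Randomisation precedes the diary and EMA week that is the baseline for two primary sleep outcomes, and the plan does not say the arm is withheld from families until that week ends

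*Combined protocol and SAP*

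**What the plan says.** Section 4 sets out this sequence: telephone screening, a 7-night eligibility diary, an in-person visit with the KSADS and questionnaires, another 7-night diary to time the saliva sampling, the DLMO overnight, and then: "After the overnight, the participant will be randomized and complete a further 7 night sleep diary and answer phone calls". The stated reason for the extra diary is that it should cover the same days as EMA. The section continues: "These measures will be the basis of the primary and secondary outcomes. Treatment will commence one week later".

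On the timing of randomisation, Section 2.1 says: "A project coordinator will conduct randomization after all eligibility assessments are completed". On concealment and blinding it says: "Sequentially numbered, opaque, sealed envelopes will be generated using a computer-generated random number list" and "Assessors will be blind to treatment allocation". It does not mention youth or parents, or when the result of the draw is disclosed.

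Section 3.2.1 makes weeknight total sleep time and bedtime primary and the weeknight-weekend discrepancies secondary. Section 3.4.2 provides one EMA week before treatment and one after. Section 5 codes Time=0 as pre-treatment, not pre-randomisation, and takes the Time by Treatment interaction as the treatment effect.

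**The concern.** A change-from-baseline comparison relies on the two arms having the same expected baseline. Randomisation guarantees this for anything measured before the arm can influence it. Here the week is before treatment but after randomisation, and the diary and EMA answers are youths' own reports. A youth who already knows the arm could alter sleep, or the account of it, during that week.

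The two arms could prompt different reactions. TranS-C is a sleep intervention. Of the comparator sessions, Section 2.3.2 says: "There will be no explicit focus on sleep except briefly mentioning sleep as a common contributor to each topic". Blinding the assessors does not remove this risk, because the person reporting is the youth.

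At stake are two primary outcomes, the diary discrepancies and all EMA scores. The credibility/expectancy questionnaire is given at the end of the second session (Section 3.6), so it cannot show what families expected during the baseline week.

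**Working it through.** **1. Do Sections 2.1 and 4 conflict?** No. Eligibility is settled by the screening diary and the in-person visit, both before the overnight. Randomising after the overnight satisfies Section 2.1. Neither section places randomisation after the baseline outcome week.

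**2. Which outcomes are exposed?**

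| Outcome | When Time=0 is collected | Exposed? |
|---|---|---|
| Weeknight total sleep time, bedtime (primary) | Diary week after randomisation | Yes |
| Weeknight-weekend discrepancies | Same diary week | Yes |
| All EMA scores | Same week; the only pre-treatment EMA week | Yes |
| DLMO | Overnight, before randomisation | No |
| CMEP, youth self-report composite (primary) | Apparently at or before the in-person visit | Probably not |

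Two earlier diaries exist, one for eligibility and one for DLMO timing. No text names either as Time=0.

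**3. How a Time=0 difference enters the estimate.** Let D0 and D1 be the TranS-C minus PE differences in means at Time=0 and Time=1, signed so that benefit is positive. The interaction estimates D1 − D0.

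- Arm unknown during the week: the expected D0 is 0, and the interaction estimates D1.
- Arm known, causing a difference b at Time=0 that is not added again at Time=1: the interaction estimates D1 − b.
- Same reaction in both arms: b = 0, and the interaction is unaffected. The within-arm pre-to-post changes, which Section 5 also reports, would still be shifted.

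If TranS-C youth begin to improve early, b is positive and the effect is diluted. If knowing the arm makes their baseline look worse relative to PE, b is negative and the effect is inflated.

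**4. The plan's own figure.** Inputs from Section 5: d = 0.48, significance 0.05, power 80%; two-sided assumed. n per arm = 2(1.960 + 0.842)² / 0.48² = 68.1, rounded up to 69. This matches the plan. The noncentral t calculation at 69 per arm gives 79.9%.

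**5. Illustration only.** The documents give no value for b, so the values below are assumed, in the SD units of d. Applying 0.48 to a single diary outcome is a further assumption, because Section 5 averages it over sleep duration and five health outcomes. Two-sided t-test at 0.05, 69 per arm:

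| b | Apparent d = 0.48 − b | Chance of rejection | Chance of rejection if D1 = 0 |
|---|---|---|---|
| −0.10 | 0.58 | 92.3% | 9.0% |
| −0.05 | 0.53 | 87.1% | 6.0% |
| 0 | 0.48 | 79.9% | 5.0% |
| 0.05 | 0.43 | 70.8% | 6.0% |
| 0.10 | 0.38 | 60.1% | 9.0% |

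For negative b the higher rejection rate reflects bias, not added power. The table shows how the contrast responds to b. It is not evidence that b differs from zero.

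**The case against.** The strongest reply is that this is silence about disclosure, not a shown flaw. Figure 1, which illustrates study flow, is not shown and the consent pages were removed; either could state when families are told. This stands, and it is why the point is conditional. The order of events, however, is explicit in Section 4 and does not depend on the missing pages.

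A large early change in behaviour is also unlikely. Section 2.2 requires that "this sleep pattern will have to have been present for the past 3 months", Table 1 notes that most students with delayed sleep phase found bedtimes hard to advance, and Section 2.3.1 introduces the cross-cutting modules only in the first session. This stands for behaviour. It does not rule out altered self-report.

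PE is also presented in Section 2.3.2 as a control for "beliefs and expectations about the efficacy of treatment held by the teens". If expectations are equal, the shift cancels in the interaction. That is a design intention, and nothing checks it during the baseline week.

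The diary outcomes have a pre-randomisation diary to fall back on. This stands, but the plan does not provide for using it, and EMA has no equivalent.

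A reader might also infer that the diary and EMA callers are unblinded because Section 2.1 does not name them. The documents do not support that: Section 3.4.2 itself describes the EMA calls as assessments, so the callers most naturally count among the blinded assessors.

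**Conclusion.** The point holds as a conditional risk created by the stated order of events. Randomisation precedes the week that supplies Time=0 for two primary diary outcomes, the discrepancies and all EMA scores, and no visible text withholds the arm from youth and parents during it. The conclusion rests on reading the measures named in Section 4 as that further diary plus EMA, which is the natural reading.

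A reader might infer that the baseline is biased, or that the trial loses a definite amount of power. Neither follows. With the arm concealed until session 1, this week is as good as a pre-randomisation baseline. If it is disclosed earlier, the bias equals b, whose sign and size the documents do not give. The power figures are therefore illustrative and carry no weight in judging severity. Nor does the problem reach every primary outcome, given the collection times of CMEP and the youth self-report composite.

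It is worth correcting before enrolment because a simple change removes the risk, and because a problem in the EMA baseline could not be repaired in the analysis.

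**What to change.** In Section 4, move randomisation (opening the envelope) to after the baseline diary and EMA week and before the first session. For sibling pairs, open it after the week of whichever sibling finishes last. This still satisfies Section 2.1 and keeps the diary concurrent with EMA.

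If the order must stay:

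1. State that allocation is withheld from youth and parents until the week ends.
2. Add a sensitivity analysis that uses the 7-night diary collected before the overnight as Time=0 for total sleep time, bedtime and the discrepancies. EMA has no such fallback.

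If allocation is already withheld in practice, writing that down resolves the main concern.

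Cost: a short text change, with no added visits, data or participants. The downsides are shorter notice for assigning an arm-specific therapist and, where siblings finish at different times, a short delay for one of them. That delay has to fit the one-week interval before treatment and the within-semester window in Section 4.

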## 5. DATA ANALYSIS

Sample size will be determined via power analysis. Power analyses will be conducted based on the average of Cohen's  $d$  (0.48) across estimations of the effect of treatment on sleep duration (for sleep outcomes) and the five primary health outcomes. Specifically, for sleep outcomes Cohen's  $d$  will be calculated from the pre-post deviation scores across TranS-C and Psychoeducation conditions. For the five health domains we will use: our pilot data for emotional health and behavioral health recent meta-analyses for cognitive health and physical health; and unpublished data from a collaborator's lab for the impact of poor sleep on social interactions. G\*Power 3.1 was used to estimate sample size using Cohen's  $d = 0.48$ , assuming significance of 0.05 and power of at least 80%. Sixty nine participants are needed for each condition. We will recruit 20% more for potential attrition. There will be no interim analyses.

Data analysis will be conducted in Stata 14 (StataCorp, 2015). All analyses will be adjusted for age and sex, which will be the stratification factors used during randomization. Using intent-to-treat, multilevel modeling with maximum likelihood estimation with the assumption of missing at random will be used to examine continuous outcomes. The fixed component of the model will include stratification factors (age and sex), an indicator for time period (Time=0 pre-treatment, Time=1 post-treatment), an indicator for treatment condition (Treatment=1 TranS-C, Treatment=0 PE), and a Time by Treatment interaction term. The random part of the model will include a subject-specific random intercept and a time and subject-specific error term. The treatment effect of interest will be the interaction, representing the difference in mean change from pre-treatment to post-treatment between TranS-C and PE. The model will also provide estimates of the mean pre-to-post change in the PE condition (coefficient of Time) and in the TranS-C condition (coefficient of Time plus interaction coefficient), and the significance of these changes will also be reported regardless of the significance of the interaction because PE may be an active control and can be beneficial. Using Hochberg's procedure, the outcomes will be considered two subfamilies of analyses. The error rate in each subfamily will be controlled under 0.025 using the Hochberg's step-up procedure, so that the overall family-wise error rate will not exceed 0.05.

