#### **3.2. Sleep Outcomes**

##### **3.2.1 Sleep Diary.**

An a priori decision was made to investigate weeknight average total sleep time (TST) and bedtime (BT) average as primary outcomes to best capture the sleep problems of interest. Secondary outcomes will be the discrepancy between weeknight and weekends for TST, BT, and waketime (WUP). Trained research assistants will phone the participants each morning to collect their sleep diary. In scheduling the call, the participants will specifically be told to not use the call as an alarm clock and to select a time as close as possible to rise time but after they are already out of bed. The training of the research assistants will specifically include not engaging in conversation other than collecting the sleep diary data. (See Table 2 for calculations of sleep diary variables).

Other secondary outcomes will be *Sleepiness Scale*, *Pittsburgh Sleep Quality Index (PSQI)* and *CBCL Sleep Composite (parent report)*.

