#### **3.3. Circadian Outcomes**

##### **3.3.1 Children's Morningness-Eveningness Preferences Scale (CMEP)**

CMEP will be a primary outcome. Scores range from 10 (Extreme evening preference) to 43 (Extreme morning preference).

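### The stated 80% power is calculated at 0.05, but every outcome is tested at 0.025 or stricter, so per-outcome power with 69 per arm is at most about 71%

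*Combined protocol and SAP*

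**What the plan says.** Section 5 (Data Analysis) of the combined protocol and SAP sizes the trial from a single standardised effect, Cohen's d = 0.48. This is an average over the effect on sleep duration and on "the five primary health outcomes". The calculation was run "assuming significance of 0.05 and power of at least 80%. Sixty nine participants are needed for each condition". An allowance follows: "We will recruit 20% more for potential attrition". Sidedness is not stated. The paragraph does not mention multiplicity, and does not say whether power refers to each outcome or to at least one outcome.

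The following paragraph of the same section sets the testing rule: "the outcomes will be considered two subfamilies of analyses", and "The error rate in each subfamily will be controlled under 0.025 using the Hochberg's step-up procedure", giving an overall family-wise rate of 0.05. The subfamily members are not listed. The quantity tested is the Time by Treatment term: "The treatment effect of interest will be the interaction, representing the difference in mean change from pre-treatment to post-treatment between TranS-C and PE".

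Elsewhere the plan names as primary "weeknight average total sleep time (TST) and bedtime (BT) average as primary outcomes" (section 3.2.1), states that "CMEP will be a primary outcome" (section 3.3.1), and labels the five-domain youth self-report composite as primary (section 3.4.1).

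**The concern.** Two adjacent paragraphs use different significance levels. The power claim is true only at 0.05, a level at which the plan never declares an outcome significant. A single-comparison calculation based on one average d reads naturally as per-outcome power, and so implies a type II error of at most 20% for each outcome at d = 0.48. Under the plan's own rule that error is larger. A null result on a primary outcome would then be read as coming from a better-powered test than was actually run. False-positive control is not in question.

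**Working it through.** **Inputs.** From section 5: d = 0.48, significance 0.05, power at least 80%, n = 69 per arm, 20% extra recruitment, and 0.025 per subfamily under Hochberg. From section 2.1: 1:1 allocation. Two-sided testing is inferred, because a one-sided 0.05 test would need only 54 to 55 per arm.

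**Step 1: reproduce the plan's figure.** Normal approximation, n per arm = 2(z₁₋α/₂ + z₁₋β)²/d²:

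- 2 × (1.960 + 0.842)² / 0.48² = 68.1, rounded up to 69. This matches the plan.
- The noncentral t calculation gives 70.
- Power at 69 per arm and 0.05 is 80.5% (normal) or 79.9% (t).

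**Step 2: the most lenient level in the testing rule.** With m outcomes in a subfamily, Hochberg compares the largest p-value with 0.025, the next with 0.025/2, and so on, down to 0.025/m for the smallest. An outcome is rejected only if its p-value is at or below a threshold that is met, and no threshold exceeds 0.025. Power at 0.025 is therefore an upper bound for any single outcome, for every m.

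**Step 3: power at the level used.** The noncentrality is d√(n/2) = 0.48 × √34.5 = 2.819, with 136 degrees of freedom.

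| Two-sided level | Power, 69 per arm (t) | Normal approximation |
|---|---|---|
| 0.05 | 79.9% | 80.5% |
| 0.025 | 70.9% | 71.8% |
| 0.025/3 = 0.00833 | 55.8% | 57.2% |
| 0.025/5 = 0.005 | 48.9% | 50.5% |
| 0.025/8 = 0.00313 | 42.8% | 44.6% |

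At 0.025, 80% power needs 84 analysed per arm (t; 83 by the normal approximation). With 69 analysed, the effect detectable with 80% power is d = 0.53.

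**Step 4: power under Hochberg itself.** Assumption: one subfamily holds total sleep time, bedtime and CMEP (m = 3), and the other holds the five health domains (m = 5). A single subfamily of all eight is shown as a variant. Simulation used t statistics, 200,000 draws per scenario and correlations of 0, 0.3 and 0.5, with 69 per arm.

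| Subfamily size | Per-outcome power, all at d = 0.48 | Per-outcome power, only one effect real |
|---|---|---|
| 3 | 65% | 56% |
| 5 | 60% | 49% |
| 8 | 53–55% | 43% |

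Normal-approximation tests give about 1 to 2 points more for m = 3 and m = 5.

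**Step 5: the attrition allowance.** 69 × 1.2 = 82.8, so 83 per arm. If nobody were lost, power at 0.025 would be 79.6% (t) or 80.3% (normal). Under Hochberg with all effects real it would be 75–76% (m = 3) and 71–73% (m = 5). Reading the allowance as 69/0.80 = 87 per arm gives 81.6% (t) at 0.025, again only with no loss.

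**The case against.** - **Power may mean at least one outcome.** On that reading the claim largely stands. With all effects real and correlation 0 to 0.5, the chance of at least one rejection is 81–92% for m = 3 and 83–97% for m = 5. The plan does not define power this way, however. Its hypothesis (section 1) expects improvement in sleep and circadian function and lower risk across all five domains. Per outcome is still a reading rather than the plan's own words, and the plan should say which it means.
- **The ceiling depends on the scale of d.** This is the strongest point. A t-test with d = 0.48 matches the Time by Treatment contrast if d is standardised on change scores. Section 5 gives that scale for sleep only; the health-domain effects come from pilot, meta-analytic and unpublished sources with no scale given. If d were on the raw-score scale, the effect on change would be 0.48/√(2(1−r)), where r is the pre-post correlation, which the documents do not give. Power at 0.025 with 69 per arm would be 54.8% at r = 0.3, 70.9% at r = 0.5 and 91.4% at r = 0.7. The 71% is therefore conditional on a change-score d, the only scale the plan states. The mismatch of levels remains at any r.
- **The extra recruitment covers the gap.** Whether 83 per arm reaches 80% turns on the approximation (79.6% or 80.3%), so that margin proves nothing. What matters is that the plan assigns the surplus to attrition.
- **The 0.025 could be one-sided.** That would restore about 80%, but the plan reaches 0.025 by splitting 0.05 over two subfamilies.
- **Subfamily membership is unknown.** This is true, and secondary outcomes could make the subfamilies larger. It affects the Hochberg figures but not the 71% bound.

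**Conclusion.** The concern holds. The 69 per condition reproduces, but the power attached to it belongs to a level the testing rule never uses. With 69 analysed per arm, a two-sided test and d = 0.48 on the change scale, per-outcome power is at most about 71% (70.9% by t, 71.8% by normal approximation), so type II error is about 29% or more rather than 20%. This bound does not depend on subfamily size. The figures of about 65% and 60% (all effects real) and 56% and 49% (one real) rest further on assumed subfamilies of three and five. Type I error control is sound. This should be fixed, but it does not invalidate the design.

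**What to change.** Restate the power paragraph in section 5 at the levels used and list the members of each subfamily. Suggested text, with bracketed items to be completed or recomputed for the actual subfamily sizes:

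> A sample of 69 per condition provides about 80% power for one outcome with d = 0.48 at a two-sided level of 0.05. Outcomes are tested in two Hochberg subfamilies at 0.025 each: [list the members]. Power is stated per outcome, with d on the pre-to-post change scale. With 69 analysed per condition and d = 0.48 it is at most 71%; the effect detectable with 80% power at 0.025 is d = 0.53. Under Hochberg it is [65% for 3 outcomes, 60% for 5] if every outcome in the subfamily has d = 0.48, and [56%, 49%] if only one does.

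If the sponsor means power for at least one outcome, the paragraph should say so and give the assumed correlations. If the health-domain effects are not on the change scale, it should give their scale and the pre-post correlation used.

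The cost is SAP wording and a less favourable stated power. Enrolment, tests and type I error control do not change.

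### Maximum likelihood with no stated small-sample reference makes the Time by Treatment test slightly anti-conservative, so the 0.05 family-wise limit is not strictly guaranteed (minor)

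*Combined protocol and SAP*

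**What the plan says.** Everything relevant is in section 5 (Data Analysis). The estimator is named: "multilevel modeling with maximum likelihood estimation with the assumption of missing at random will be used to examine continuous outcomes". The model has two time points, with fixed effects for age, sex, time, treatment and their interaction. For the random part, "The random part of the model will include a subject-specific random intercept and a time and subject-specific error term". The estimand is also explicit: "The treatment effect of interest will be the interaction, representing the difference in mean change from pre-treatment to post-treatment between TranS-C and PE".

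On multiplicity, the outcomes form two subfamilies. Within each of them, the plan states: "The error rate in each subfamily will be controlled under 0.025 using the Hochberg's step-up procedure". From this it draws a firm limit across both: "so that the overall family-wise error rate will not exceed 0.05".

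On size, "Sixty nine participants are needed for each condition", and "We will recruit 20% more for potential attrition".

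The section does not say whether the interaction is tested by a Wald or a likelihood-ratio test, or whether a normal or a t reference is used. It gives no degrees-of-freedom method and does not list the outcomes in each subfamily.

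**The concern.** ML estimates variances without allowing for the fixed effects that were estimated. In a two-wave model this shrinks the standard error of the interaction by a known factor. If the resulting ratio is then referred to the normal distribution, a second small error is added in the same direction. Both make p-values too small and intervals too narrow, and neither depends on clustering, unequal variances or any other model failure.

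The plan states the family-wise limit as a firm property. The named estimator, with the reference left open, does not strictly deliver it. A result lying almost on a Hochberg threshold could turn on a choice that the plan has not made.

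**Working it through.** **Inputs.** From section 5: ML, two time points, random intercept, 0.025 per subfamily, d = 0.48, alpha 0.05, power 80%, 69 per arm. From section 2.1: 1:1 allocation. Assumed because the plan does not say: the reference distribution, the make-up of the subfamilies, and the correlation between outcomes.

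**The plan's own figures.** Error budget: 0.025 + 0.025 = 0.05, as stated. Sample size, two-sided: n = 2(1.960 + 0.842)²/0.48² = 2 × 7.85/0.2304 = 68.1, so 69 per arm, as stated. N is 138, and 138 × 1.2 = 165.6, so about 166 recruited.

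**Standard error.** With complete pairs, the interaction estimate is the difference in mean change. Age and sex enter only as main effects, so they cancel from the changes. ML uses SS/N for the variance of change; REML uses SS/(N-2). The ratio of standard errors is √((N-2)/N):
- N = 138: √(136/138) = 0.9927, or 0.7% too small.
- N = 166: √(164/166) = 0.9940, or 0.6% too small.

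**True level at nominal 0.025, N = 138, 136 degrees of freedom.**
- ML with normal reference: the cut-off on the t scale is 2.2414 × 0.9927 = 2.2251; 2P(t > 2.2251) = 0.0277.
- ML standard error with t reference: 2.2665 × 0.9927 = 2.2500; level 0.0261.
- ML likelihood-ratio test, LR = N·log(1 + t²/(N-2)): the cut-off is t = √(136 × (e^(5.0239/138) - 1)) = 2.2455; level 0.0264.
- REML standard error with normal reference: level 0.0266.
- REML with t: 0.0250 exactly.

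Of the 0.0027 excess under ML with a normal reference, the ML standard error alone accounts for about 0.0011 and the normal reference alone for about 0.0016.

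Hochberg's step-up procedure compares the largest p-value with the full 0.025 and reaches its strictest threshold last. The relative excess grows as the threshold tightens. For ML with a normal reference, nominal 0.0083 becomes 0.0098 and nominal 0.005 becomes 0.0061. With the ML standard error and t, nominal 0.005 becomes 0.0053. At N = 166, the level at 0.025 under ML with a normal reference is 0.0273.

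**Missing post-treatment data.** Model fits to 30,000 simulated trials, with 83 per arm and 17% missing, gave 0.0276 for ML with a normal reference and 0.0252 for REML with t at nominal 0.025.

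**Family-wise error.** Simulated with N = 138 and all nulls true. The assumed subfamilies are 3 outcomes (weeknight total sleep time, bedtime, CMEP) and 5 outcomes (the youth self-report domains). Repeat runs differ by about 0.1 point.

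| Between-outcome correlation | ML, normal | ML SE, t | REML, t |
|---|---|---|---|
| 0 | 5.8% | 5.1% | 4.9% |
| 0.2 | 5.6% | 5.0% | 4.8% |
| 0.4 | 5.1% | 4.6% | 4.3% |
| 0.5 | 4.8% | 4.3% | 4.1% |

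With just one true null in each subfamily, tested at the full 0.025, ML with a normal reference gives 5.5% if the two are independent, 5.1% at correlation 0.5 and 4.8% at 0.7.

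**The case against.** The strongest reply is that the named estimator does little of the damage. Set against REML with t, the ML standard error adds about 0.2 to 0.3 of a point to family-wise error. Most of the higher figures come from a normal reference, which section 5 never mentions. This stands: a reader might infer that choosing ML by itself pushes family-wise error well past 5%, and the documents do not support that.

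Second, whether 5% is exceeded at all depends on correlations that the documents do not give, and near-independence is doubtful. Section 3.4.1 draws both the cognitive and the social domain partly from the same social adjustment scale, and all five domains sit in one youth self-report cluster. Table 2 computes total sleep time from time in bed, which starts at bedtime. This stands as well. A reader might infer an established breach, but the figures show only that the limit is not guaranteed. The 3 + 5 split, and the 0.0083 and 0.005 thresholds that follow from it, are assumptions. The unlisted subfamilies leave more open in the error-rate statement than ML versus REML does.

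Third, large-sample ML inference at 138 to 166 participants is conventional, and the excess is under one percentage point. That bears on severity. It does not remove the point, because the limit is stated without condition and each way of testing from the ML fit examined here exceeds nominal per test.

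**Conclusion.** The point holds as a minor one. At 138 complete pairs the ML standard error is about 0.7% too small, and the true level at nominal 0.025 lies between 0.0261 and 0.0277 depending on the unstated reference. The 0.05 family-wise limit is therefore not strictly guaranteed. Under the assumed 3 + 5 split with all nulls true, the rate is about 5.1% to 5.8% for ML with a normal reference at correlations of 0 to 0.4 and below 5% from about 0.5. It is about 5.1% or less with the ML standard error and t.

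The exact figures assume complete pairs, equal arms, normal errors, a positive intercept variance and independent participants; same-arm sibling pairs were not modelled. No conclusion would be expected to change unless a p-value fell almost on a threshold.

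**What to change.** In section 5, replace maximum likelihood estimation with restricted maximum likelihood (REML). Add that the Time by Treatment interaction will be tested, and its interval formed, from a t distribution with Kenward-Roger or Satterthwaite degrees of freedom. The model, the estimand and the missing-at-random assumption do not change. In the simulated settings, REML with t kept family-wise error at or below 0.05. The same paragraph is the place to list the outcomes in each subfamily.

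The change needs no extra participants or data, but it is not free in nominal terms. At the 0.025 level and N = 138, intervals widen by about 1.9% (2.2665/2.2251 = 1.0186). Nominal power at d = 0.48, ML with a normal reference against REML with t:

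| Alpha | N = 138 | N = 166 |
|---|---|---|
| 0.05 | 80.8% to 79.9% | 87.3% to 86.7% |
| 0.025 | 72.3% to 70.9% | 80.5% to 79.6% |
| 0.005 | 51.5% to 48.9% | 61.9% to 59.8% |

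The power given up came from a test that rejected slightly too often. The choice should be fixed before outcome data are seen.
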